14.3.3 Hypothesis Testing/ Assessment of Efficacy

Further details of the planned statistical methods presented below will be provided in the study Statistical Analysis Plan (SAP). The purpose of the SAP is to further elaborate the statistical methods described in the protocol and describe analysis conventions to guide the statistical programming work. Any changes to the final SAP will be documented. Unless otherwise specified, the hypothesis testing will be conducted by the difference of means for a two-sample two-sided test with a significance level of 0.050.

The Evaluable Period for the outcome variables will be weeks 1, 4, 8 and 12. During each Evaluable Period an ordinal value based on IGA, CEA, PSA scores will be collected. The probability of improving will be the criteria to assess the superiority of the drug over the vehicle. The null and alternative statistical hypotheses for the primary effectiveness endpoints are given by:

(*H₀*) : The null hypothesis is that the probability of improving (across the scale) with drug T (*Pr_T*) is less than or equal to the probability of improving with vehicle (*Pr_V*)

$$H_0: PrT \leq PrV; PrT - PrV \leq 0$$

(*H_a*): The alternative hypothesis is that the probability of improving with drug T (*Pr_T*) is greater than to the probability of improving with vehicle (*Pr_V*).

$$H_a: PrT > PrV; PrT - PrV > 0$$

The change from baseline score of Skindex-16 will be compared among treatment at weeks 1, 4, 8 and 12 by a repeated measure analysis.

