3.1.2 Exploratory Objectives

To assess the efficacy of B244 in subjects with mild to moderate rosacea.

- Proportion of subjects with IGA improvement at Week 8 relative to baseline.
- Proportion of subjects with CEA improvement at Week 8 relative to baseline.
- Change in IGA score from Baseline to Week 8.
- Change in CEA score from Baseline to Week 8.
- Proportion of Subjects with improvement in IGA or CEA at Week 1, Week 4, and Week 12.
- Change in Skindex 16 patient reported outcome from Baseline to Week 1, Week 4, Week 8, and Week 12.
- Proportion of subjects with change in PSA at Week 1, Week 4, Week 8 and Week 12 from Baseline.
- Evaluation of Telangiectasia Score at Baseline/Day 1 and Week 8

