8.3 Efficacy Analysis

All efficacy endpoints are exploratory endpoints.

Assessment of Superiority:

- IGA treatment success, defined as “clear” or “almost clear” with a 2-grade improvement in IGA score from baseline to the end of treatment (Week 8).
- CEA treatment success, defined as “clear” or “almost clear” with a 2-grade improvement in CEA score from baseline to the end of treatment (Week 8).

Superiority will be based on the proportion of subjects for whom treatment was successful. The comparison will be through a continuity-corrected Z-tests. The Evaluable Period for the outcome variables will be weeks 1, 4, 8 and 12. The superiority of the drug over the vehicle will be tested at week 8 based on the probability of

improvement from baseline with a continuity-corrected Z-tests comparing the change from baseline of treatments vs Placebo. For all other evaluable periods, descriptive statistics for the change from baseline will be shown.

The null and alternative statistical hypotheses for the primary effectiveness endpoints are given by:

(*H*₀): The null hypothesis is that the probability of improving (baseline to week 8) with drug T (*Pr*_T) is less than or equal to the probability of improving with vehicle (*Pr*_V).

$$H_0: Pr_T - Pr_V \leq 0; Pr_T$$

(*H*_a): The alternative hypothesis is that the probability of improving with drug T (*Pr*_T) is greater than to the probability of improving with vehicle (*Pr*_V).

$$H_a: Pr_T > Pr_V; Pr_T - Pr_V > 0$$

For testing the superiority, the following SAS code will be used:

```
proc freq data = dataset;
  tables treat*outcome/riskdiff (equal);
run;
```

- Change of Skindex 16 patient reported outcome from Baseline to Week 1, Week 4, Week 8 and Week 12

The change from baseline score of Skindex-16 will be compared among treatments at Week 12 using an ANOVA, to test the Skindex 16 score change from Baseline to Week 12 for the two treatments. Also, descriptive stats will be used to assess the change from Baseline to Week 1, 4, 8 & 12.

- Change of IGA score at Baseline to Week 1, Week 4, Week 8 and Week 12.
- Change of CEA score at Baseline to Week 1, Week 4, Week 8 and Week 12.
- Change of PSA score at Baseline to Week 1, Week 4, Week 8 and Week 12.

Descriptive stats will be used to show the change from Baseline to Week 1, 4, 8 & 12.

- Supplemental Analysis

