 Supplemental analysis will be performed based on any IGA or CEA improvement from Baseline including p-values for the change from Baseline to Week 8 within each treatment group, and IGA and CEA for the subgroup of patients that had a baseline IGA or CEA of 3.

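### SAP v2.0 adds within-arm p-values for IGA and CEA change and leaves the B244-versus-vehicle contrast unspecified for any improvement and for the baseline-3 subgroup

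*SAP*

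**What the plan says.** The protocol frames efficacy as a comparison of arms. Section 14.3.3 states: "The probability of improving will be the criteria to assess the superiority of the drug over the vehicle". Its null hypothesis is that the probability of improving on drug does not exceed that on vehicle. The first efficacy objective in SAP v2.0 Section 3.1.2 is "Proportion of subjects with IGA improvement at Week 8 relative to baseline", followed by the same for CEA.

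SAP v2.0 Section 8.3 opens with "All efficacy endpoints are exploratory endpoints". It then sets out between-arm testing. For IGA and CEA treatment success (score 0 or 1 with a 2-grade improvement), "Superiority will be based on the proportion of subjects for whom treatment was successful". It also plans a Week 8 superiority test on the probability of "improvement from baseline with a continuity-corrected Z-tests comparing the change from baseline of treatments vs Placebo", with hypotheses on the difference between arms and PROC FREQ risk-difference code.

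The section ends with a paragraph that SAP v1 does not contain. It opens: "Supplemental analysis will be performed based on any IGA or CEA improvement from Baseline". What this analysis must contain is then described in these words: "including p-values for the change from Baseline to Week 8 within each treatment group". The paragraph also asks for results in patients whose baseline IGA or CEA was 3. It names no test for the within-arm p-values and no contrast for the subgroup.

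**The concern.** A within-arm test asks whether scores moved from baseline. The trial asks whether they moved more on B244 than on vehicle. Subjects enter on IGA 2-3 and CEA 2-3, and both arms receive cleanser and moisturizer, so some improvement without a drug effect is plausible in either arm. A small p-value in the B244 arm cannot separate a B244 effect from regression to the mean or a vehicle effect. A significant result in one arm and not in the other is not evidence that the arms differ.

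The outcome concerned, any improvement, corresponds to the first-listed efficacy objectives. If the only p-values expressly attached to it are within-arm, the report could show significant improvement on B244 without the randomized contrast beside it.

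**Working it through.** **What the between-arm tables cover.** With entry scores of 2 or 3, the possible improvements at end of treatment (Week 8) are:

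| Change | Any improvement | Score 0/1 (Table 14.2.8.1) | 2-grade (Table 14.2.6.1) |
|---|---|---|---|
| 2 to 1 | yes | yes | no |
| 2 to 0 | yes | yes | yes |
| 3 to 2 | yes | no | no |
| 3 to 1 | yes | yes | yes |
| 3 to 0 | yes | yes | yes |

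These two shells, repeated for CEA and for the PP population, are the only ones in SAP v2.0 with a risk difference. Neither matches any improvement: the 2-grade table omits 2 to 1 and 3 to 2, and the 0/1 table omits 3 to 2. In subjects with baseline 3 the two shells count the same people and both miss the 1-grade improvers. Table 14.2.1.1 counts 1-, 2- and 3-grade changes by arm with no test. No shell addresses the baseline-3 subgroup.

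**Inputs for the illustration.**
- Subjects per arm: SAP Sections 4.3 and 8.1 give 130 enrolled with 20% dropout, 130 × 0.80 = 104, and 104 / 2 = 52. As a check on the plan's own figure, 52 per arm with 33% versus 10% at two-sided 0.05 gives 82.4% power without continuity correction, and 78.0% by exact enumeration of the corrected Z-test (unpooled standard error assumed). The stated 80% lies between. This does not bear on the point beyond supplying n.
- Two-sided 5% level: SAP Section 6.4.
- Within-arm test: not named in the SAP; an exact sign test is assumed.
- Improvement and worsening rates: not in the documents; a range is assumed, the same in both arms.

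**Formula.** With i improvers and j worseners among 52, the sign test gives p = 2 × P(Binomial(i + j, 0.5) ≤ j) when i > j. The chance r that an arm shows significant improvement is the multinomial probability of all (i, j) with i > j and p < 0.05. With independent, identical arms, the chance that B244 is significant and vehicle is not is r(1 − r).

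**Hand check.** At 20% improving and 5% worsening, the expected counts are 52 × 0.20 = 10.4 and 52 × 0.05 = 2.6. Ten against two gives p = 2 × (1 + 12 + 66) / 4096 = 0.039, significant. Ten against three gives p = 2 × (1 + 13 + 78 + 286) / 8192 = 0.092, not significant. A rejection rate near one half is what to expect.

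**Results, no difference between arms.**

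| Improve / worsen | r, each arm | r(1 − r) |
|---|---|---|
| 10% / 10% | 0.011 | 0.011 |
| 10% / 5% | 0.073 | 0.068 |
| 20% / 5% | 0.499 | 0.250 |
| 30% / 10% | 0.565 | 0.246 |
| 40% / 10% | 0.857 | 0.123 |
| 30% / 5% | 0.870 | 0.113 |

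For comparison, the continuity-corrected Z-test between arms uses (|p1 − p2| − 1/n) / √{[p1(1 − p1) + p2(1 − p2)] / n}. By exact enumeration at n = 52 with equal true rates, it wrongly favours B244 in 1.2% of trials at a 10% improvement rate, 1.5% at 20%, 1.6% at 30% and 1.8% at 40%.

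**The case against.** A reader might infer that SAP v2.0 has replaced the randomized comparison with within-arm tests. It has not. The supplemental sentence uses the word including, which adds and removes nothing, and Section 8.3 retains the Week 8 test against vehicle with hypotheses on the probability of improving. On one reading, that test already covers any improvement, and the 0/1 tables miss only the 3-to-2 changes.

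A reader might also infer that significance on B244 but not on vehicle will be taken as proof of superiority. No passage makes that a decision rule; superiority is defined between arms. The 25% figure is also the mathematical ceiling of r(1 − r), reached only when r is near one half.

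Nor do the documents establish that both arms will improve. Entry scores are bounded above and below and are required at both Screening and Baseline, which limits one-directional regression to the mean. Protocol Section 9.1 makes the cleanser and moisturizer available as needed, with moisturizer optional. The subgroup text does not say its comparison is within-arm.

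All of this stands, and it narrows the point without removing it. Section 8.3 introduces superiority through 2-grade success and then speaks of improvement without equating or separating the two. For the outcome expressly called any improvement, the only p-values named are within-arm, and no shell supplies the contrast. The 3-to-2 change that both risk-difference shells miss is the 1-grade improvement in the baseline-3 subgroup.

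**Conclusion.** The point holds in limited form. The planned within-arm p-values do not answer the trial's question and can be significant with identical arms. The between-arm contrast is not clearly specified for any improvement and is not specified at all for the baseline-3 subgroup. The existing superiority tests are unaffected.

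The size depends on net improvement, which the documents do not give. Over the assumed rates, each arm is significant between 1% and 87% of the time, and the one-arm-only pattern occurs between 1% and 25% of the time. These figures rest on a sign test the SAP does not name, on 52 evaluable subjects per arm, and on assumed rates. They illustrate the risk and do not predict it.

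Because efficacy is exploratory and this analysis is supplemental, it is a change that should be made, not a flaw in the trial's primary conclusion, which concerns safety.

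**What to change.** In the Supplemental Analysis paragraph of SAP v2.0 Section 8.3, replace the within-arm p-values with wording to this effect:

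> For IGA and for CEA, the proportion of mITT subjects with an improvement of at least 1 grade from Baseline to Week 8 will be compared between B244 and vehicle by the risk difference (B244 minus vehicle), its 95% CI and the continuity-corrected Z-test. The same comparison will be made for IGA in subjects with baseline IGA 3 and for CEA in subjects with baseline CEA 3. Within-arm change will be reported descriptively, without p-values.

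This also settles what improvement means for this outcome and which baseline score defines each subgroup. The analysis stays labelled supplemental and exploratory. The cost is SAP wording and a few added table shells (any improvement and the baseline-3 subgroup, each for IGA and CEA). The data are already collected, and Section 8.3 already contains risk-difference code to build on.

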8.4 Sensitivity Analysis

A sensitivity analysis will be performed by Multiple Imputation Regression Analysis using the following factors: treatment, age, gender, race, baseline IGA, baseline CEA, baseline

PSA, smokers/non-smokers and the results of the same variable from previous visits. The Proc MI SAS code will be used to perform the analysis based on the mentioned factors.

10 APPENDIX

10.1 APPENDIX A: Tables

10.1.1 General

Display Number	Title	Population	Unique/Repeat
14.1.1.1	Subject Enrollment and Disposition	All Subjects	Unique
14.1.1.2	Subject Enrollment and Disposition	Enrolled Subjects	Unique
14.1.1.3	Analysis Population and Exclusions	All Subjects	Unique
14.1.2.1	Summary of Protocol Deviations (PD)/Violations (PV)	mITT	Unique
14.1.2.2	Summary of Protocol Deviations (PD)/Violations (PV)	Safety	Repeat
14.1.3.1	Summary of Demographic and Baseline Characteristics	mITT	Unique
14.1.3.2	Summary of Demographic and Baseline Characteristics	PP	Repeat
14.1.3.3	Summary of Demographic and Baseline Characteristics	Safety	Repeat
14.1.4.1	Summary of Vital Sign	mITT	Unique
14.1.4.2	Summary of Vital Sign	PP	Repeat
14.1.4.3	Summary of Vital Sign	Safety	Repeat
14.1.5.1	Summary of Physical Examination	mITT	Unique
14.1.5.2	Summary of Physical Examination	PP	Repeat
14.1.5.3	Summary of Physical Examination	Safety	Repeat
14.1.6	Summary of Study Drug Accountability: Dose Dispensed & Collected by Visit	Safety	Unique
14.1.7.1	Summary of Study Drug Compliance	Safety	Unique
14.1.7.2	Summary of Percent Compliance based on Cumulative Net Weight of Study Drug	Safety	Unique
14.1.8	Summary of Prior or Concomitant Medications	Safety	Unique
14.1.9	Summary of Medical History	Safety	Unique
14.1.10	Summary of Substance Abuse	Safety	Unique
14.1.11	Summary of Dairy Details	Safety	Unique

Table 14.1.1.1
 Subject Enrollment and Disposition
 All Subjects

Disposition	B244 Topical Spray n (%)	Placebo n (%)	All Patients n (%)
Screened	xx	xx	xx (xx.x)
Randomized	xx	xx	xx (xx.x)
Treated	xx	xx	xx (xx.x)
Completed Study	xx	xx	xx (xx.x)
Discontinued	xx	xx	xx (xx.x)
Screen Failure	xx	xx	xx (xx.x)
Withdrawal of consent	xx	xx	xx (xx.x)
In the opinion of the Investigator, it is not in the subject's best interests to continue in the study	xx	xx	xx (xx.x)
Pregnancy	xx	xx	xx (xx.x)
Occurrence of an Adverse Event (AE) or Serious Adverse Event (SAE), which, in the opinion of the Investigator warrants discontinuation of the subject from the study	xx	xx	xx (xx.x)
The subject is lost to follow-up	xx	xx	xx (xx.x)
Other	xx	xx	xx (xx.x)

NOTE: The percentages are based on the number of All subjects.

Subjects may have more than one reason for discontinuation, and they are counted more than once.

Snapshot Data DD-MMM-YYYY

Source: <Dataset>

Program Name: <Pgm name>

Table 14.1.1.2
 Subject Enrollment and Disposition
 Enrolled Subjects

Disposition	B244 Topical Spray n (%)	Placebo n (%)	All Patients n (%)
Randomized	xx (xx.x)	xx (xx.x)	xx (xx.x)
Treated	xx (xx.x)	xx (xx.x)	xx (xx.x)
Completed	xx (xx.x)	xx (xx.x)	xx (xx.x)
Completed Week 1	xx (xx.x)	xx (xx.x)	xx (xx.x)
Completed Week 4	xx (xx.x)	xx (xx.x)	xx (xx.x)
Completed Week 8	xx (xx.x)	xx (xx.x)	xx (xx.x)
Completed Week 12	xx (xx.x)	xx (xx.x)	xx (xx.x)
Discontinued	xx (xx.x)	xx (xx.x)	xx (xx.x)
Withdrawal of consent	xx (xx.x)	xx (xx.x)	xx (xx.x)
In the opinion of the Investigator, it is not in the subject's best interests to continue in the study	xx (xx.x)	xx (xx.x)	xx (xx.x)
Pregnancy	xx (xx.x)	xx (xx.x)	xx (xx.x)
Occurrence of an Adverse Event (AE) or Serious Adverse Event (SAE), which, in the opinion of the Investigator warrants discontinuation of the subject from the study	xx (xx.x)	xx (xx.x)	xx (xx.x)
The subject is lost to follow-up	xx (xx.x)	xx (xx.x)	xx (xx.x)
Other	xx (xx.x)	xx (xx.x)	xx (xx.x)

NOTE: The percentages are based on the number of Randomized subjects.

Subjects may have more than one reason for discontinuation, and they are counted more than once.

Snapshot Data DD-MMM-YYYY

Source: <Dataset>

Program Name: <Pgm name>

Table 14.1.1.3
 Analysis Population and Exclusions
 All Subjects

Number of Subjects	B244 Topical Spray n (%)	Placebo n (%)	All Patients n (%)
Enrolled	xx	xx	xx
Randomized	xx	xx	xx
Included in Safety Population	xx	xx	xx (xx.x%)
Reasons for Exclusion from Safety Population			
	xx	xx	xx (xx.x%)
	xx	xx	xx (xx.x%)
Included in Full Analysis Set	xx	xx	xx (xx.x%)
Reasons for Exclusion from Safety Population			
	xx	xx	xx (xx.x%)
Included in Per Protocol Population	xx	xx	xx (xx.x%)
Reasons for Exclusion from Per Protocol Population			
Lost To Follow Up	xx	xx	xx (xx.x%)
Major Deviation	xx	xx	xx (xx.x%)
Not 50% Ip Compliant	xx	xx	xx (xx.x%)
Screen Failure	xx	xx	xx (xx.x%)
Withdrawal of Consent By Subject	xx	xx	xx (xx.x%)

NOTE: The percentages are based on the number of All subjects.

Snapshot Data DD-MMM-YYYY

Program Name: <Pgm name>

Source: <Dataset>

Table 14.1.2.1
 Summary of Protocol Deviations (PD)/Violations (PV)
 mITT Population

Deviation/Violation Description of Violation/deviation	Deviation/Violation Category “Major” or “Minor”	B244 Topical	Placebo	All
		Spray n (%) xx	n (%) xx	Patients n (%) xx

NOTE: The percentages are based on the number of ITT Population.

Source: <Dataset>

Snapshot Data DD-MMM-YYYY
 Program Name: <Pgm name>

Repeat for Safety Population

Table 14.1.3.1
 Summary of Demographic and Baseline Characteristics
 mITT Population

Variable	Statistic	B244 Topical Spray n (%)	Placebo n (%)	All Patients n (%)
Age	N	xx	xx	xx
	Mean (SD)	xx.x (xx.xxx)	xx.x (xx.xxx)	xx.x (xx.xxx)
	Min, Max	xx.x, xx.x	xx.x, xx.x	xx.x, xx.x
Sex				
	Male	N (%) xx (xx.x)	xx (xx.x)	xx (xx.x)
	Female	N (%) xx (xx.x)	xx (xx.x)	xx (xx.x)
Ethnicity				
	Hispanic or Latino	N (%) xx (xx.x)	xx (xx.x)	xx (xx.x)
	Not Hispanic or Latino	N (%) xx (xx.x)	xx (xx.x)	xx (xx.x)
Race				
	American Indian or Alaskan Native	N (%) xx (xx.x)	xx (xx.x)	xx (xx.x)
	Asian	N (%) xx (xx.x)	xx (xx.x)	xx (xx.x)
	Black or African American	N (%) xx (xx.x)	xx (xx.x)	xx (xx.x)
	Native Hawaiian or Other Pacific Islander	N (%) xx (xx.x)	xx (xx.x)	xx (xx.x)

Protocol: RB244-001
 Confidential

STATISTICAL ANALYSIS PLAN

 Version 2
 02-Apr-19

Variable	Statistic	B244 Topical Spray n (%)	Placebo n (%)	All Patients n (%)
White	N (%)	xx (xx.x)	xx (xx.x)	xx (xx.x)
Other	N (%)	xx (xx.x)	xx (xx.x)	xx (xx.x)

NOTE: The percentages are based on the number of ITT Population.

Snapshot Data DD-MMM-YYYY

Program Name: <Pgm name>

Source: <Dataset>

Repeat for PP and Safety population

 Table 14.1.4.1
 Summary of Vital Signs,
 mITT Population

Visit	Vital Sign	Statistic	B244 Topical Spray n (%)	Placebo n (%)	All Patients n (%)	
Baseline	Height	N	xx	xx	xx	
		Mean (SD)	xx.x (xx.xxx)	xx.x (xx.xxx)	xx.x (xx.xxx)	
		CV	xx.x	xx.x	xx.x	
		Median	xx.x	xx.x	xx.x	
		Min, Max	xx.x, xx.x	xx.x, xx.x	xx.x, xx.x	
	Weight	N	xx	xx	xx	
		Mean (SD)	xx.x (xx.xxx)	xx.x (xx.xxx)	xx.x (xx.xxx)	
		CV	xx.x	xx.x	xx.x	
		Median	xx.x	xx.x	xx.x	
		Min, Max	xx.x, xx.x	xx.x, xx.x	xx.x, xx.x	
		Temperature	N	xx	xx	xx
			Mean (SD)	xx.x (xx.xxx)	xx.x (xx.xxx)	xx.x (xx.xxx)
	CV		xx.x	xx.x	xx.x	
	Median		xx.x	xx.x	xx.x	
	Min, Max		xx.x, xx.x	xx.x, xx.x	xx.x, xx.x	
	Heart Rate	N	xx	xx	xx	
		Mean (SD)	xx.x (xx.xxx)	xx.x (xx.xxx)	xx.x (xx.xxx)	
		CV	xx.x	xx.x	xx.x	
		Median	xx.x	xx.x	xx.x	
		Min, Max	xx.x, xx.x	xx.x, xx.x	xx.x, xx.x	
		Systolic BP	N	xx	xx	xx
Mean (SD)			xx.x (xx.xxx)	xx.x (xx.xxx)	xx.x (xx.xxx)	
CV	xx.x		xx.x	xx.x		
Median	xx.x		xx.x	xx.x		

Visit	Vital Sign	Statistic	B244 Topical	Placebo	All Patients	
			Spray n (%)	n (%)	n (%)	
Repeat for every visit showing Change from Baseline	Diastolic BP	CV	xx.x	xx.x	xx.x	
		Median	xx.x	xx.x	xx.x	
		Min, Max	xx.x, xx.x	xx.x, xx.x	xx.x, xx.x	
		N	xx	xx	xx	
		Mean (SD)	xx.x (xx.xxx)	xx.x (xx.xxx)	(xx.xxx)	
		CV	xx.x	xx.x	xx.x	
		Median	xx.x	xx.x	xx.x	
		Min, Max	xx.x, xx.x	xx.x, xx.x	xx.x, xx.x	
						xx.x
						(xx.xxx)

NOTE: The percentages are based on the number of ITT Population.

CRF pages 05-06

Source: <Dataset>

Snapshot Data
 DD-MMM-
 YYYY
 Program Name:
 <Pgm name>

Repeat for PP and Safety population

Table 14.1.5.1
 Summary of Physical Examination,
 mITT Population

Visit	Physical Examination	Statistic	B244 Topical	Placebo	All Patients
			Spray n (%)	n (%)	n (%)
Baseline					
	General Appearance				
	Normal	N (%)	xx (xx.x)	xx (xx.x)	xx (xx.x)
	Abnormal	N (%)	xx (xx.x)	xx (xx.x)	xx (xx.x)
	Heart Cardiovascular				
	Normal	N (%)	xx (xx.x)	xx (xx.x)	xx (xx.x)

Protocol: RB244-001
 Confidential

STATISTICAL ANALYSIS PLAN

 Version 2
 02-Apr-19

Visit	Physical Examination	Statistic	B244 Topical		All Patients n (%)
			Spray n (%)	Placebo n (%)	
	Abnormal	N (%)	xx (xx.x)	xx (xx.x)	xx (xx.x)
	Lungs				
	Normal	N (%)	xx (xx.x)	xx (xx.x)	xx (xx.x)
	Abnormal	N (%)	xx (xx.x)	xx (xx.x)	xx (xx.x)
	Gastrointestinal				
	Normal	N (%)	xx (xx.x)	xx (xx.x)	xx (xx.x)
	Abnormal	N (%)	xx (xx.x)	xx (xx.x)	xx (xx.x)
	Ear/Nose/Throat				
	Normal	N (%)	xx (xx.x)	xx (xx.x)	xx (xx.x)
	Abnormal	N (%)	xx (xx.x)	xx (xx.x)	xx (xx.x)
	Extremities				
	Normal	N (%)	xx (xx.x)	xx (xx.x)	xx (xx.x)
	Abnormal	N (%)	xx (xx.x)	xx (xx.x)	xx (xx.x)
	Skin				
	Normal	N (%)	xx (xx.x)	xx (xx.x)	xx (xx.x)
	Abnormal	N (%)	xx (xx.x)	xx (xx.x)	xx (xx.x)

 Repeat for
 every week

 NOTE: The percentages are based on the
 number of ITT Population.

 CRF pages 05-06
 Source: <Dataset>

Snapshot Data DD-MMM-YYYY

Program Name: <Pgm name>

Repeat for PP and Safety populations

Table 14.1.6
 Summary of Study Drug Accountability: Dose Dispensed & Collected by Visit
 Safety Population

Weight of the Dose	Visit	Statistic	B244 Topical		All Patients n (%)
			Spray n (%)	Placebo n (%)	
Dose Dispensed	Baseline	N	xx	xx	xx
		Mean (SD)	xx.x (xx.xxx)	xx.x (xx.xxx)	xx.x (xx.xxx)
		CV	xx.x	xx.x	xx.x
		Median	xx.x	xx.x	xx.x
		Min, Max	xx.x, xx.x	xx.x, xx.x	xx.x, xx.x

 Repeat for Dose
 Collected by Visits

N: Number of Patients

CRF pages 28-30

Snapshot Data DD-MMM-YYYY

Mean(SD) : Mean (Standard Deviation),CV:

Program Name: <Pgm name>

Coefficient of Variance..

Source: <Dataset>

Table 14.1.7.1
 Summary of Study Drug Compliance
 Safety Population

	Statistic	B244 Topical Spray n (%)	Placebo n (%)	All Patients n (%)
Number of Subjects with Compliance				
Yes	N (%)	xx (xx.x)	xx (xx.x)	xx (xx.x)
No	N (%)	xx (xx.x)	xx (xx.x)	xx (xx.x)
If No, Applications Missed				
Missed Applications	N	xx	xx	xx
	Mean (SD)	xx.x (xx.xxx)	xx.x (xx.xxx)	xx.x (xx.xxx)
	CV	xx.x	xx.x	xx.x
	Median	xx.x	xx.x	xx.x
	Min, Max	xx.x, xx.x	xx.x, xx.x	xx.x, xx.x

 Applications: Number of applications per patients/day
 (expected 4 Pumps twice a Day)

 Snapshot Data DD-MMM-
 YYYY

CRF pages 30

 Compliance: The expected amount of study drug used
 per week is approximately 7.84 g/week for 8
 sprays/application per day

 Source:
 <Dataset>

 Program Name: <Pgm
 name>

Table 14.1.7.2
 Summary of Percent Compliance based on Cumulative Net Weight of Study Drug
 Safety Population

Protocol: RB244-001
 Confidential

STATISTICAL ANALYSIS PLAN

 Version 2
 02-Apr-19

Statistic	B244 Topical			All Patients n (%)
	Spray n (%)	Placebo n (%)		
Cumulative Net Weight of Study Drug				
N	xx	xx	xx	xx
Mean (SD)	xx.x (xx.xxx)	xx.x (xx.xxx)	xx.x (xx.xxx)	xx.x (xx.xxx)
CV	xx.x	xx.x	xx.x	xx.x
Median	xx.x	xx.x	xx.x	xx.x
Min, Max	xx.x, xx.x	xx.x, xx.x	xx.x, xx.x	xx.x, xx.x
Percent Compliance greater than 50%				
Yes	N (%)	xx (xx.x)	xx (xx.x)	xx (xx.x)
No	N (%)	xx (xx.x)	xx (xx.x)	xx (xx.x)

Applications: Number of applications per patients/day (expected 4 Pumps twice a Day)

Snapshot Data DD-MMM-YYYY

CRF pages 30

The cumulative amount of study drug exposure will be estimated by calculating the difference between the weight of the 2 bottles of drug at the time the drug was dispensed at Baseline/Week 4 and the weight of the 2 bottles at Week 4/Week 8. Differences will be summed together.

Program Name: <Pgm name>

Source: <Dataset>

% Compliance: The net weight of study drug divided by 1.12g/Day * Number of Days in the Study

Table 14.1.8
 Summary of Prior or Concomitant Medications,
 Safety Population

WHO-DD ATC Class Level 1 WHO-DD ATC Class Level 2 WHO-DD Preferred Term	B244 Topical Spray n (%)	Placebo n (%)	All Patients n (%)
Number of subjects with at least one prior medication	xx (xx.x)	xx (xx.x)	xx (xx.x)
WHO-DD ATC Class Level 1	xx (xx.x)	xx (xx.x)	xx (xx.x)

Protocol: RB244-001
 Confidential

STATISTICAL ANALYSIS PLAN

 Version 2
 02-Apr-19

WHO-DD ATC Class Level 2	xx (xx.x)	xx (xx.x)	xx (xx.x)
WHO-DD Preferred Term 1	xx (xx.x)	xx (xx.x)	xx (xx.x)
WHO-DD Preferred Term 2	xx (xx.x)	xx (xx.x)	xx (xx.x)
etc.			
WHO-DD ATC Class Level 1	xx (xx.x)	xx (xx.x)	xx (xx.x)
WHO-DD ATC Class Level 2	xx (xx.x)	xx (xx.x)	xx (xx.x)
WHO-DD Preferred Term 1	xx (xx.x)	xx (xx.x)	xx (xx.x)
WHO-DD Preferred Term 2	xx (xx.x)	xx (xx.x)	xx (xx.x)
etc.			

NOTE: The percentages are based on the number of Safety Population.

 CRF page 11
 Source: <Dataset>

Snapshot Data DD-MMM-YYYY

Program Name: <Pgm name>

Table 14.1.9
 Summary of Medical History
 Safety Population

WHO-DD SOC WHO-DD Preferred Term	B244 Topical Spray n (%)	Placebo n (%)	All Patients n (%)
Number of subjects with at least one Medical History	xx (xx.x)	xx (xx.x)	xx (xx.x)
WHO-DD SOC	xx (xx.x)	xx (xx.x)	xx (xx.x)
WHO-DD Preferred Term	xx (xx.x)	xx (xx.x)	xx (xx.x)
WHO-DD Preferred Term 1	xx (xx.x)	xx (xx.x)	xx (xx.x)
WHO-DD Preferred Term 2	xx (xx.x)	xx (xx.x)	xx (xx.x)
etc.			

NOTE: The percentages are based on the number of Safety Population.

 CRF pages
 Source: <Dataset>

Snapshot Data DD-MMM-YYYY

Program Name: <Pgm name>

Table 14.1.10
 Summary of Substance Abuse
 Safety Population

Statistics	B244 Topical Spray	Placebo N (xxx)	All Patients N (xxx)
------------	--------------------------	--------------------	-------------------------

		N (xxx)		
Total Number of Substance Abuse	n	xx	xx	xx
		xx	xx	xx
		xx	xx	xx
Number of Subjects with Substance Abuse History	n (%)	xx (xx.x)	xx (xx.x)	xx (xx.x)
		xx (xx.x)	xx (xx.x)	xx (xx.x)
		xx (xx.x)	xx (xx.x)	xx (xx.x)

NOTE: The percentages are based on the number of Safety Population.

CRF pages
 Source: <Dataset> Snapshot Data DD-MMM-YYYY
 Program Name: <Pgm name>

Table 14.1.11
 Summary of Diary Details
 Safety Population

		B244 Topical		
Statistics		Spray N (xxx)	Placebo N (xxx)	All Patients N (xxx)
Number of Subjects with diary Dispensed	n	xx	xx	xx
Number of Subjects with diary Collected	n	xx	xx	xx
		xx	xx	xx
Number of Subjects with Sunscreen use	n (%)	xx (xx.x)	xx (xx.x)	xx (xx.x)
Number of Subjects with Makeup use	n (%)	xx (xx.x)	xx (xx.x)	xx (xx.x)

NOTE: The percentages are based on the number of Safety Population.

CRF pages
 Source: <Dataset> Snapshot Data DD-MMM-YYYY
 Program Name: <Pgm name>

